Step 1: In ANC: Healthcare providers provide counseling on HIV prevention and treatment at each ANC visit including HIV testing, as part of standard of care. In post-natal care and well-baby visits women may not receive regular HIV testing and messages and will receive this within step 2 (with study counselor). Following their ANC visit, enrolled women will be invited to attend the study site in each MOU to do the follow-up visit including the ACASI survey and prescription and adherence counseling (if on PrEP).

Step 2: ACASI survey at each visit in a private study room

Step 3: In the study room, the study counselors will provide PrEP-specific counseling including adherence counseling for those on PrEP (and management of side effects), or counseling about the risks and benefits of PrEP for women not yet on PrEP. Women not on PrEP will be asked if they are interested in starting PrEP at this visit.

Step 4: STI testing: At 3rd trimester visit and first postpartum visit, participants self-collect a vaginal swab for STI testing (chlamydia, gonorrhea and trichomonas vaginalis using Cepheid® point of care testing). Participants will be treated if diagnosed with a STI according to National Guidelines. They will receive a partner notification letter to bring their partner in for treatment as well.

Step 5 (for women on PrEP): At each visit the study counselor will ask, and record responses, all participants on PrEP about any side effects associated with TDF/FTC, including diarrhea, nausea, fatigue, headache and rash (which are seen in about 10% of participants during the initiation of therapy). We will encourage participants to contact the study nurse if they experience side effects between visits.

For participants on PrEP, the study nurse performs a blood draw for creatinine clearance and a finger prick for DBS testing for adherence measures and (if applicable for this visit). See Table 1 for study calendar.

Step 6: PrEP provision (for 1 or 2 months) and appointment reminder

Follow-up & retention: Tracing information will be taken at the enrolment visit and updated at each study visit. Retention activities will focus on scheduled measurement visits. Following our established approach in this setting, we will provide reminder calls to participants before their measurement visits, and initiate tracing, including home visits, for women who do not attend the measurement visit within one week of the scheduled visit.

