- **DBS:** Dried blood spots will be prepared from finger pricks every two months in women on PrEP to evaluate adherence.
 - DBS cards will be prepared and stored following standard protocols and stored at -80°C for analysis at the end of the study with the clinical pharmacodynamic laboratory of [name] at UCT. Using techniques developed by [name] at University of Colorado [16] adherence will be defined as red blood cells containing TDF-DP ≥ 40 ng/dl which is indicative of daily dosing [16]. As supplementary measures of PrEP adherence, we will use self-reported items that we will adapt from previous studies (including visual analogue scales as well as 3-day, 30-day and last visit recall questionnaires) (22-25), and pharmacy refill records to compare objective versus subjective measures and report on the effectiveness of each measure in correlation to the true measures of TDF-DP. We will determine final dosing and measures following reporting from ongoing PK studies of pregnant women on PrEP (e.g. Impaact 2009).

Laboratory tests in all women in the cohort:

- **STI testing (baseline, 3rd trimester and first postpartum visit):** Self-collected vaginal swab kits will be provided to all participants along with an explanation for their use. Swabs will be analyzed using on-site testing equipment (GeneXpert; Cepheid ®) for rapid testing of chlamydia, gonorrhoea and trichomonas vaginalis. If they test positive, they will be treated by the nurse/midwife in ANC or postpartum care and a referral for her partner to receive STI treatment in the clinic.
- **HIV testing.** As part of the standard of care, all pregnant and breastfeeding women will be tested for HIV using serial rapid HIV tests at each antenatal and postnatal care visit. In addition, PrEP-PP study staff will have a stock of rapid HIV test kits to ensure that women get tested at each study visit.
 - **Seroconversion.** If a woman, infant or partner seroconverts at any point during the study, they will be referred to the clinician on duty to initiate ART, following counseling about PMTCT, breastfeeding, disclosure, and ART adherence, per the SA National Protocols [17]. Seroconverted women will be censored from the remainder of the study and referred to the clinic to initiate ART.

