 - If a woman seroconverts while on PrEP, there may be a risk of ART resistance, though research has demonstrated that the risk of ART resistance is very low [12, 13]. In the case of seroconversion, Drs [name] and [name] will follow seroconverters with the study team to evaluate if the patient achieves viral suppression within 6 months of ART start, and if not, she will be referred for specialist attention for testing for ART resistance and clinical follow-up.

Adverse events:

- **Maternal adverse events:** We will collect data on maternal adverse events by asking mothers about intercurrent medical events, which will be reviewed by an obstetrician, including any hospitalizations or illnesses. We will also track and report changes in creatinine or other toxicities in women on PrEP.
- **Infant adverse events:** We will collect data on infant adverse events by asking mothers about infant health or intercurrent medical events, which will be reviewed by a pediatrician.
 - Adverse birth outcomes will include infants that were small for gestational age, pre-term births, miscarriage and stillbirths.

Table 1: PrEP-PP cohort measures by participant study month

Participant study month	Pregnancy						Post-partum											
	1	2	3	4	5	6	7	8	9	10	11	12	13	14	15	16	17	18
Study enrollment and consent of consecutive sample of HIV-negative pregnant women (N=220)	X																	
PrEP group, individual (or couples counseling where applicable) and information, education, counseling materials on PrEP in pregnancy and breastfeeding in local languages (at each visit)	X	X	X	X	X	X	X		X		X		X		X			X
Routine ANC and postnatal care, well-baby visit follow-up (as available in standard of care), including rapid HIV testing, pregnancy, and birth outcomes	X	X	X	X	X	X	X		X		X		X		X			X
ACASI survey to collect: behavioral acceptability, knowledge, and substance use data	X	X	X	X	X	X	X		X		X		X		X			X
Screening at enrolment for Hepatitis B surface antigen. If HBsAg+ = excluded from study	X																	
Laboratory testing for STIs (chlamydia and gonorrhoea) & treatment if positive	X				X		X											
For women on PrEP:																		
Laboratory tests of creatinine (if eGFR<60ml/min cannot continue on PrEP, refer to return in 1 month for re-test)	X			X			X								X			X
PrEP pharmacy refills and adherence supportive counseling monthly (for first 3 months on PrEP) then every 2 months for following months	X	X	X		X		X		X		X		X		X			X

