DBS taken for TDF-DP adherence measures (bi-monthly in participants on PrEP)	X	X	X		X		X		X		X		X		X			X
In-depth interviews for 20 participants							X											X
Collect study data on: (1) PrEP counseling, (2) PrEP medication when requested, (3) regular appointments, (4) IEC materials, (5) adherence counselling and support by facility, through patient ACASI survey at every study visit	X	X	X	X	X	X	X	X	X	X	X	X	X	X	X	X	X	X

Training, quality assurance and supervision:

1. *Existing DOH staff:* We will conduct an on-site half day training for existing counselors, nurses and midwives and Managers in the two study sites on the study protocol to ensure that they understand and support the integration of the study in their facility.

- a. **Inclusion of interviews for healthcare providers in health facility to understand their knowledge of and attitudes around PrEP:** We seek to interview existing health care providers including nurses, counselors, midwives and managers to understand their knowledge about PrEP, HIV prevention in pregnancy and any attitudes about PrEP that may affect future integration of

PrEP and PrEP uptake in the facility. We will interview approximately 20 health care providers and have one focus group in those providers in isiXhosa or Afrikaans. We will record, translate and transcribe their responses and analyze the results thematically in order to develop interventions around provider training and support.

2. *Study staff:* We will hire 2 counselors, 2 nurses, 2 coordinators who will receive a 3-day training program and they will be required to complete the entire training course. After completion of the training, the study PI will observe the counselor and nurse completing each step of the intervention with a mock patient. Upon satisfactory completion of observed sessions, the counselors and nurses will be certified to conduct the study intervention and will receive a completion certificate.
3. *Quality assurance* will occur on three levels. Day-to-day monitoring, supervision, and support of counselors will be carried out by the Study Coordinators (from UCT—1 per facility). The Study Coordinator will provide on the job training to ensure that counselors and nurses respect the study protocol. Adherence to the counseling protocol will be established by the Study Coordinator who will sit in on a random subsample of 20% of counseling sessions to ensure that counselors are adhering to study protocols.

Sources of data

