The primary analysis will focus on measuring the distribution of women across the PrEP cascade including: initiation, retention and adherence. **PrEP initiation** will be based on a woman’s uptake of PrEP and allow for stoppage and re-initiation; **PrEP retention** will be defined as not missing >1 visit among those on PrEP (with separate analyses of PrEP stoppage). For **PrEP adherence** for women on PrEP we will measure both **perfect adherence** (i.e. level of objective adherence throughout pregnancy and breastfeeding periods) as well as “**prevention-effective**” adherence (i.e. adherence before and during times of sexual activity) in participants through objective and subjective measures to evaluate agreement between the two measures, and the level of under- or over-reporting. Primary adherence analyses will use objective measures (TDF-DP from DBS) taken on all those who enrolled and initiated PrEP; subsidiary analyses will consider (i) other adherence measures and (ii) multiple imputation for missing adherence data.

- **Use of PrEP will be measured** through alternate definitions of the main outcomes (e.g. adherence by self-report versus adherence by pharmacy refill), compared using measures of agreement and will be analyzed as independent models to contrast estimated associations.

- **Measurement of prevention-effective execution:** Execution refers to PrEP adherence during a time when at-risk sex happens. It is calculated by: number of doses reported, or recorded/number of expected doses based on HIV risk and PrEP initiation/discontinuation
- **Prevention-effective continuation:** Prevention-effective continuation describes the duration of PrEP use during periods of HIV risk and references the absolute time of use during pregnancy and breastfeeding periods. We will adapt the methodology from previous PrEP studies in SA including FEM-PrEP to create a semi-ordinal composite adherence score from blood specimens from DBS every 2-months.

Table 2: Study measures for PrEP-PP

Primary Outcomes	Measurement	Source	Frequency
PrEP initiation	# of women who initiate PrEP over time / total # of women in active cohort = proportion of women who initiate PrEP	Electronic provider log (REDCap)	Daily entry, weekly analysis

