PrEP retention	# of women on PrEP who return for study visits (do not miss more than 1 visit) / total # of women in active cohort who are prescribed PrEP= proportion of women on PrEP who are retained in PrEP study	Electronic provider log (REDCap)	Daily, analysis weekly
PrEP adherence-subjective	# of women taking PrEP, who self-report taking their medication daily (& pill count to confirm this) during periods of sexual risk over time / total woman-time on PrEP in active cohort = PrEP adherence rate (subjective)	Electronic provider log (REDCap)	Daily, analysis weekly
PrEP adherence-objective	# of women taking PrEP who have >80% levels at >40ng/mL TDF-DP (indicating dosing in past 24 hours) at 3 rd trimester, delivery, and 6 weeks postpartum (and during sexual risk periods during that time) / total woman-time on PrEP in active cohort = PrEP adherence rate (objective)	Lab analysis of TDF-DP measures	Quarterly
Secondary Outcomes			
Predictors of attrition at key steps in the PrEP cascade	Individual, pill/study and disease specific predictors of attrition	ACASI	ACASI: Every study visit
HIV outcomes	HIV testing data: HIV-uninfected, HIV-positive for mother and child (if mother seroconverts)	Electronic provider log (REDCap)	Every visit
Health outcomes and adverse events	Any side-effects, creatinine, any negative maternal or neonatal outcomes (for mother and infant)	Electronic provider log (REDCap)	During routine lab tests and visits

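### Blood spots and refills share the same visits, so analysing only spots taken, or imputing without refill history, probably overstates adherence among women who start PrEP

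*Combined protocol and SAP*

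**What the plan says.** Section 6 states: "Primary adherence analyses will use objective measures (TDF-DP from DBS) taken on all those who enrolled and initiated PrEP". One of two subsidiary analyses is "multiple imputation for missing adherence data". No imputation model, auxiliary variable or missing-data assumption is given, and nothing says how a scheduled DBS that was not taken is to count.

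Section 5 restricts sampling to current users: "Dried blood spots will be prepared from finger pricks every two months in women on PrEP to evaluate adherence". Follow-up step 6 reads "PrEP provision (for 1 or 2 months) and appointment reminder". In Table 1, the rows "PrEP pharmacy refills and adherence supportive counseling monthly (for first 3 months on PrEP) then every 2 months for following months" and "DBS taken for TDF-DP adherence measures (bi-monthly in participants on PrEP" are marked in the same study months.

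Table 2 defines the objective measure differently. Its numerator is the number "of women taking PrEP who have >80% levels at >40ng/mL TDF-DP (indicating dosing in past 24 hours", assessed in the third trimester, around delivery and six weeks after birth. Its denominator is "total woman-time on PrEP in active cohort = PrEP adherence rate (objective". Objective 1(3) in section 2 concerns the proportion adhering among women who initiate PrEP.

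**The concern.** A woman who misses a visit gives no DBS and collects no pills. A woman who has stopped PrEP is not sampled even if she attends. In both cases likely non-use appears as an absent value, not a low one. An analysis of DBS taken then describes the women who kept coming and kept taking PrEP. Imputation that assumes missing at random and ignores refill history gives the absent women roughly the same drug levels. The mixed-effects probit and GEE models in section 6 do not remove the problem, because in standard form they too assume that missingness does not depend on unobserved adherence.

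Objective adherence is a primary outcome, and section 1 says that the results are to inform policymakers on adding PrEP to antenatal and postnatal care. An upward error would make that look more successful than it was.

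**Working it through.** The plan gives no expected adherence, missing-DBS rate or precision target for this outcome, so there is no figure to reproduce.

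**Schedules (Table 1).** Refill months are 1, 2, 3, 5, 7, 9, 11, 13, 15, 18. DBS months are 1, 2, 3, 5, 7, 9, 11, 13, 15, 18. All 10 coincide. Month 1 is enrolment, which leaves nine later occasions.

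**Size of the bias.** Let p be adherence among DBS taken, m the share of due DBS that are missing, and q adherence among the women with missing DBS.

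- True adherence among all due = p(1 − m) + qm.
- Available-case analysis, or imputation at random without refill history, gives about p.
- Overstatement = m(p − q).

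All values of p, m and q below are assumptions. With p = 60%:

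| m | q = 0: true (overstated by) | q = 30% | q = 60% |
|---|---|---|---|
| 10% | 54% (6 points) | 57% (3) | 60% (0) |
| 20% | 48% (12) | 54% (6) | 60% (0) |
| 30% | 42% (18) | 51% (9) | 60% (0) |

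With q = 0 and m = 10-30%, the overstatement is 4-12 points at p = 40% and 8-24 points at p = 80%.

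**Against sampling error.** The 95% half-width at 50% is 1.96 × √(0.5 × 0.5 / 220) = 6.6 points if all 220 initiate, and 1.96 × √(0.5 × 0.5 / 132) = 8.5 points if 132 (60%) do. The bias can match or exceed it.

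**Simulation.** The model has nine intervals, 60% adherence while supplied, 20% of visits missed, and no pills in the interval after a missed visit. A shared trait links attendance to adherence, with strength 0, 0.7 or 1.5 on the probit scale.

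| Link | Truth | Available case | Imputed using previous refill | All missing = non-adherent |
|---|---|---|---|---|
| none | 49% | 49% | 49% | 40% |
| moderate (0.7) | 53% | 59% | 57% | 48% |
| strong (1.5) | 55% | 65% | 59% | 52% |

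Two results matter for the fix:

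- Where the previous visit was attended, adherence behind a missed DBS was 60%, 43% and 34% in the three settings. Where the previous refill was also missed, it was 0. A first missed DBS is therefore not evidence of non-use, whereas a second consecutive one normally is.
- The simulation samples every attender, including women returning after a gap. If such women do not count as being on PrEP and are not sampled, the available-case figure with no link would be the 60% seen while supplied, against a truth of 49%: 11 points too high.

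**The case against.** **No bias is demonstrated.** A reader might infer that both estimates are certainly too high. The documents do not support that. They give no missing rate and no adherence level for non-attenders, m(p − q) is zero when q = p, and the no-link simulation was unbiased. This stands, and the conclusion is limited to a probable direction.

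**Table 2 may already deal with it.** If woman-time without a DBS stays in the denominator, a missing DBS lowers the rate. If time without supply is excluded, the quantity is adherence while on PrEP, which is a legitimate cascade step. Both readings are possible because Table 2 does not choose. Neither clearly answers objective 1(3), which is about initiators. Section 4 censors women who are away for more than 8 weeks and cannot be traced, so an active cohort may well leave out likely non-users.

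**Running out is measured elsewhere.** Retention, stoppage, continuation, time to loss and refill-based adherence are all planned. They describe the attrition but do not correct the objective figure, and the retention definition tolerates one missed visit.

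**The imputation could be a good one.** Refill records are collected and would help. In the simulation they removed part of the bias, not all of it. Self-report and pill counts for the same interval come from the same visit, so they are usually missing along with the DBS.

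**Tracing will limit missingness.** Section 5 plans reminder calls and home visits, and transport is reimbursed. This should lower m, but it does not supply a rule for the DBS still missing.

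**Scoring all missing DBS as failures would be wrong too.** This stands. Supply lasts until about the next visit, and the rule gave results below the truth in every setting simulated. It is a lower bound.

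**Conclusion.** The concern holds as a probable upward bias in the proportion of initiators who adhere, arising from a visit structure that ties missing DBS to missing supply and from a plan with no rule for it. At 60% observed adherence and 10-30% missing, the overstatement is 6-18 points if the women with missing DBS are non-adherent, 3-9 if half as adherent and 0 if equally adherent. These inputs are assumed; the documents fix none of them.

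A reader might also infer that the bias grows through follow-up. The documents do not support this: no section says when loss is greatest, and Table 2's time points end six weeks after birth, well before the 12-month close.

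The pilot status stated in section 6 does not remove the point, since estimating the cascade is the pilot's purpose.

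**What to change.** Amend the adherence paragraph of section 6 and the objective adherence row of Table 2:

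1. Define the denominator as all women who initiated PrEP and are due a DBS at each time point, whether or not they are still using it. State how censored women count. Reconcile this with Table 2's woman-time denominator, and report adherence while supplied separately.
2. Report the number of DBS expected and taken at each time point.
3. Using refill records, count a missing DBS as below threshold when the woman had no dispensed supply for the interval before it. This normally applies from the second consecutive missed refill visit, not the first.
4. Impute the other missing DBS, including failed samples and first missed visits, with refill history in the model.
5. Show available-case results and an all-missing-as-non-adherent lower bound as sensitivity analyses.

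The supply rule needs one inconsistency reconciled first: Table 1 leaves three months between the month 15 and month 18 refills, while section 5 describes provision for one or two months.

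The cost is SAP wording, with no new data collection. Section 5 stores DBS cards for analysis at study end (although Table 2 lists the measure as quarterly), so the rule can be set before results are seen. The downside is a lower headline figure that is conservative for women with leftover pills or PrEP obtained elsewhere.

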Our team is comprised of highly experienced adolescent HIV prevention researchers, including [name] and [name], who have a long history of research that seeks to address the key health issues facing South African adolescent girls while at the same time protecting this vulnerable population. The research sites have considerable experience in conducting clinical research in adolescent populations.

Figure 2. HIV incidence (%) by age and sex in South Africa

[figure not shown]
[figure not shown]

Figure 3. Adolescent pregnancy in South Africa, 2010-2013

Our study, PrEP-PP (PrEP in Pregnant and Postpartum women) will determine the distribution of women across the PrEP cascade (i.e. PrEP initiation, retention, and adherence) in a cohort of HIV- pregnant and breastfeeding adolescent girls and women in two public health facilities in South Africa to inform policymakers about the efficacy of PrEP integration into antenatal (ANC) and postnatal care in high HIV incidence communities.

2. Study objectives:

The objectives of the study are to:

1. Determine the distribution of women across the PrEP cascade:
 - (1) Evaluate the proportion of pregnant and breastfeeding women who initiate PrEP out of all women offered PrEP
 - (2) Evaluate the proportion of pregnant and breastfeeding women who are retained in the PrEP cohort
 - (3) Evaluate the proportion of pregnant and breastfeeding women who initiate PrEP who adhere to PrEP using objective dried blood spot measures and subjective measures of self-reported pill count and adherence
 - (4) Evaluate the proportion of pregnant and breastfeeding women on PrEP (and not on PrEP) who acquire HIV, who transmit HIV to their infant, and who report adverse events
2. Evaluate patient and provider-level factors associated with the PrEP cascade using quantitative and qualitative approaches (including in-depth interviews)

3. Study design

To address these objectives, we will conduct an observational cohort study in 220 pregnant women who will be recruited at the first antenatal care (ANC) visit from the Gugulethu Midwife Obstetric Units in Cape Town. We will follow the enrolled women through 12-months post-delivery.

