Setting. The study will take place in two urban townships in Cape Town (Gugulethu MOU) with high HIV incidence that span the different socioeconomic, cultural, and ethnic groups in South Africa. We selected this community because of the high HIV prevalence there in pregnant and breastfeeding women, and because of the high number of mothers visiting every month for ANC and labour/delivery. Further, our team has several years' experience implementing research studies in those MOUs which will facilitate the integration of the study there. In 2017, Gugulethu saw over 3300 new ANC consultations per month, and 72% (n=2300) are HIV-negative. Considering our experience and patient flow, we are confident that at least 60 women/month per facility can be enrolled. Further, Drs. [name], [name] and colleagues have conducted research in the Gugulethu community for more than a decade and have substantial experience partnering with local health services. Building on this platform, we will use existing infrastructure in each clinic, including capacitating existing clinical providers, pharmacists and counselors, to provide PrEP care to pregnant and breastfeeding mothers. We will hire study staff to assist in the coordination, data management, and overall quality assurance of the counseling, drug provision and participation follow-up.

4. Study population

Study counselors will enroll consecutive eligible, consenting pregnant adolescent girls (≥ 16 years) and women in ANC (N=220 pregnant women) and follow them up for 12-months postpartum or until censorship for a mean of 18-months' follow-up.

Inclusion Criteria:

1. ≥ 16 years old
2. confirmed HIV-negative (using 2 rapid HIV test kits, confirmed with a 4th generation antigen HIV test),
3. lives within 20 kilometers of a clinic

4. confirmed to be pregnant
5. without psychiatric or medical contraindications to PrEP

Exclusion criteria:

Individuals not meeting the above criteria or meeting any of the following criteria will be excluded:

- Concurrent enrolment in another HIV-1 vaccine or prevention trial
- Medical hospitalization in the past year for any reason
- Receipt of TB treatment within the past 30 days
- History of renal disease
- Exhibiting psychotic symptoms (including hallucinations, suicidal or homicidal ideations, or violent behaviour)
- Currently or history of taking an anti-psychotic medication (such as for treatment of bipolar disorder, schizophrenia, or postpartum psychosis following a previous pregnancy)

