Step 11: Participants will receive counselling on the risks and benefits of PrEP. Following the counseling they will be asked: “Do you want to start taking PrEP today to prevent HIV? You will need to take it daily for it to be effective.” Her response will be recorded.

If yes:

1. The nurse will provide the participant with a 1-month supply of TDF-FTC and invite her to return in 1 month for her next study visit.
2. Nurses will provide contact information to the participant and ask her to call to report any side effects or adverse events while on PrEP, and nurse will track and report serious adverse events to study PIs, Pediatrician, and Obstetrician to decide on how to treat women and infants who have adverse events.

If she says she does not want to start PrEP, woman will be in the deferred PrEP arm:

1. The nurse will schedule her to return in 1 month for the follow-up visit

Step 12: Participants will receive study staff contact information, instructions to call with any questions, and will be scheduled for their next visit in 1 month for the next study visit

Step 13: Participants will receive study staff contact information, instructions to call with any questions, and will be scheduled for their next visit in 1-week to return when test results have returned from the laboratory

Step 14: The study counselor will provide the mother with an appointment card and invitation for her partner to return to receive couples’ HIV testing and counseling (if in a relationship). The session will end by encouraging the client to implement her/his risk-reduction plan (including PrEP if applicable and consistent condom use, couples testing) to prevent HIV acquisition.

Step 15: The participant will receive up to R250 per visit including reimbursement for the participant’s time, transportation and including their refreshments during the study. Further, we will combine the study visits with existing ANC or post-partum/well-baby visits to minimize the travel to the facilities outside of normal clinical checkups.

2. For follow up return visits:

Follow up visits will be monthly until birth (to coincide with ANC visits) then every two months after birth (to coincide with post-partum, well-baby visits).

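### The primary retention proportion in Table 2 rests on an undefined active cohort and a missed-visit rule, so women lost or withdrawn may not be counted as non-retained

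*Combined protocol and SAP*

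**What the plan says.** Table 2 (section 6) heads initiation, retention and adherence as primary outcomes. The retention row counts women on PrEP who return for visits and miss no more than one, and divides by "total # of women in active cohort who are prescribed PrEP= proportion of women on PrEP who are retained in PrEP study". The initiation row reads "of women who initiate PrEP over time / total # of women in active cohort = proportion of women who initiate PrEP". Both adherence rows use woman-time in the same cohort ("total woman-time on PrEP in active cohort = PrEP adherence rate (subjective" and "total woman-time on PrEP in active cohort = PrEP adherence rate (objective"). The term active cohort appears only in Table 2 and is not defined.

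Other sections name other populations:

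- Objective 1(1), section 2: "Evaluate the proportion of pregnant and breastfeeding women who initiate PrEP out of all women offered PrEP".
- Objective 1(2), section 2: the proportion retained in the PrEP cohort.
- Section 6, text before Table 2: retention is judged among those on PrEP, with PrEP stoppage analysed separately. Primary adherence is taken on everyone who enrolled and initiated.
- Section 6, text after Table 2: every outcome is described by cumulative incidence at fixed intervals and by incidence density. Time to loss, glossed as non-retention, is modelled among women who have initiated PrEP.

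Section 4 says staff will "follow them up for 12-months postpartum or until censorship". It lists four reasons for censorship: seroconversion, moving away, transfer out of care, and loss to follow-up. Loss covers absence of more than 8 weeks in a woman who cannot be traced, and also a wish not to continue. Section 5 sets visits monthly until birth and every two months afterwards.

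**The concern.** The plan uses loss in two ways: as a reason to stop counting a woman (section 4) and as the event to be counted (section 6, after Table 2). Table 2 does not say which applies to its retention proportion. It gives no time point, only daily entry and weekly analysis, and nothing ranks it against the cumulative-incidence description.

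Section 6 presents the study as a pilot meant to estimate the PrEP cascade and factors associated with attrition. A retention figure that omits women who left would look better than the programme was. It would also disagree with the time-to-loss analysis of the same data.

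**Working it through.** The plan gives no expected initiation, loss or retention figure, so there is nothing to reproduce. The only sourced input is 220 women (sections 3 and 4). Every rate below is an assumption.

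**Denominator.** Let n be initiators, c those lost or withdrawn, and m those who stay but miss more than one visit.

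- Over all initiators, leavers counted as non-retained: (n − c − m)/n.
- Over women not censored: (n − c − m)/(n − c).
- The second exceeds the first by the factor n/(n − c).

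Assume n = 154 (70% of 220) and m = 10% of those who stay, rounded to whole women. The half-width is 1.96·√(p(1 − p)/154), with p the all-initiator proportion.

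| Loss | c | n − c | m | Retained | Not-censored | All initiators | Gap (points) | 95% half-width (points) |
|---|---|---|---|---|---|---|---|---|
| 10% | 15 | 139 | 14 | 125 | 125/139 = 89.9% | 125/154 = 81.2% | 8.8 | 6.2 |
| 20% | 31 | 123 | 12 | 111 | 111/123 = 90.2% | 111/154 = 72.1% | 18.2 | 7.1 |
| 30% | 46 | 108 | 11 | 97 | 97/108 = 89.8% | 97/154 = 63.0% | 26.8 | 7.6 |

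The not-censored figure hardly moves as loss triples. If 20% of stayers miss more than one visit, the gaps are 7.8, 16.0 and 23.8 points. At 20% loss and 10% other misses, the gap is 18.0 points with 110 initiators (79/88 = 89.8% against 79/110 = 71.8%). With 198 initiators it is 18.2 points (142/158 = 89.9% against 142/198 = 71.7%).

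**Missed-visit rule.** Two months is 2 × 30.44/7 = 8.7 weeks, so the loss threshold of more than 8 weeks is shorter than one postpartum visit interval. An untraceable postpartum woman can therefore be censored after one missed visit, before a second falls due. A woman who withdraws may have missed none. Both satisfy a rule of no more than one missed visit.

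If k of the c leavers are in this position and the rule is applied literally over all initiators, the proportion is (n − c − m + k)/n. In the 20% loss row:

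- k = 0: 111/154 = 72.1%
- k = 15: 126/154 = 81.8%
- k = 31 (the extreme): 142/154 = 92.2%

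Fixing the denominator alone therefore does not settle the matter.

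**Which censoring matters.** Only loss-type censoring raises the figure. Take 154 initiators with 15 non-retained: 139/154 = 90.3%. Removing 10 good attenders who seroconverted gives 129/144 = 89.6%, slightly lower.

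**The case against.** The best case for the plan is that active need not mean uncensored. Women consent and have blood drawn, and are offered PrEP the same day, before the renal results return (section 5, Steps 5, 10 and 11). Women positive for hepatitis B surface antigen are then excluded. Active cohort may simply mean enrolled women left after those exclusions, and then lost women stay in the denominator. Objective 1(2) and the gloss of loss as non-retention both lean towards counting leavers against retention. The cumulative-incidence statement covers every outcome, and Table 2's weekly frequency looks like monitoring. Tracing with home visits (section 5) also keeps reachable poor attenders in the cohort, where they count as non-retained.

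Much of this stands. It shows that a benign reading exists and may be the intended one. It does not show that the plan states it, and it leaves the missed-visit gap untouched. The time-to-event sentence is about factors associated with loss. It names no retention time point, and it conflicts with the censoring list.

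A reader might also infer that initiation is inflated, perhaps beyond 100%. The documents do not support that. Every participant is asked "Do you want to start taking PrEP today to prevent HIV" at baseline, and later "Women not on PrEP will be asked if they are interested in starting PrEP at this visit", so the offered and enrolled sets nearly coincide. Under a not-censored reading the figure could move either way or stay put, and a value above 100% requires lost women to be kept in the numerator but dropped from the denominator, an unlikely analysis. The adherence rows share the undefined term, but the text already fixes the primary adherence population, and no harm is shown there.

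**Conclusion.** The point holds for retention and should be fixed before analysis. As written, the Table 2 rule can overstate a primary estimate in two ways: by dropping lost and withdrawn women from the denominator, or by keeping them and letting them pass the missed-visit rule. Under the assumed rates the first gives gaps of about 9, 18 and 27 points at 10%, 20% and 30% loss, each larger than the sampling half-width. If leavers stay in the denominator and count as non-retained, the gap is zero.

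A reader might conclude that reported retention will be too high. The documents do not go that far: they leave the choice open, and they give no loss rates from which to judge its size. For initiation, the only finding is that Table 2 and Objective 1(1) should name the same denominator; no direction of bias is claimed.

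**What to change.** - Define the active cohort and keep that ratio for weekly monitoring only.
- Report primary retention at stated times, for example delivery and 12 months postpartum, as women retained divided by all women who initiated PrEP and were not excluded on baseline laboratory results. Section 5 is inconsistent on whether an eGFR below 60 mL/min at enrolment excludes a woman from the study or only from PrEP. Those passages must be reconciled before this set can be fixed.
- Count loss to follow-up and withdrawal as non-retained, whatever the number of missed visits.
- Keep women who moved, transferred or seroconverted in the denominator as separate categories, with a sensitivity analysis counting them each way.
- Report PrEP stoppage separately, as section 6 already plans.
- State that loss is an event, not censoring, in the retention curves, so that section 4, Table 2 and the modelling text agree. Name one of them as the primary result.
- Align the initiation denominator in Table 2 with Objective 1(1).

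The cost is wording and analysis code, with no new data. Reported retention may be lower than under the not-censored reading.
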